Appendix E Procedures for Main Cohort, Immediate Vaccination Group

Visit:	01 ¹	02 ²	03	04	05	06
Day:		D1	D29	D57	D113	D141
Week:		W0	W4	W8	W16	W20
Month:		M0	M1	M2	M4	M5
Procedure	Scr.	VAC1	VAC2			
Study procedures						
Screening consent (if used)	✓	—	—	—	—	—
Assessment of understanding	✓	—	—	—	—	—
Protocol consent (eConsent)	✓	—	—	—	—	—
Medical history questionnaire ³	✓	✓	—	—	—	—
SARS-CoV-2 infection risk assessment ³	✓		Weekly			
COVID-19 symptom surveillance ³	—		Weekly starts at week 2, not during week 5			
Confirm eligibility	✓	—	—	—	—	—
Obtain demographics ³	✓	—	—	—	—	—
Randomize	—	✓	—	—	—	—
SARS-CoV-2 testing questionnaire ³	—		approximately 2x per week			
End of study questionnaire ³	—	—	—	—	✓	—
Research Samples⁴						
Serum for Immunogenicity Assays and Storage	—	✓	—	✓	—	—
Serum for SARS-CoV-2 clinical serology ⁵	—	✓ ⁶	—	✓ ⁶	✓	—
Nasal swab	—		Daily ⁷			
Vaccination procedures						
COVID-19 symptom check ⁸	—	✓	✓	—	—	—
Vaccination	—	✓	✓	—	—	—

Greyed out visit column does not apply to this group.

1 Screening may occur over the course of several contacts/visits up to and including day 1, prior to vaccination.

2 Blood draws required at vaccination visits must be performed prior to vaccination.

3 Results from screening at school, if applicable, or at other locations will be captured via eDiary, please see Section 9.16.

4 From screening to the final study visit, the total blood volume to be collected from each participant will be approximately 40 mL (maximum) with a maximum of approximately 17 mL collected in a single visit.

5 For blood self-collected by a participant the maximum volume will be less than 1 mL in a single collection.

6 SARS-CoV-2 clinical serology testing may be performed on leftover blood from samples collected for immunogenicity assays. No separate blood sample is needed. If a Main cohort participant is also in the Prospective Close Contact (PCC) cohort related to

an index case or in the Case-ascertained Close Contact (CACC) cohort, one additional blood collection (self-collection) will be performed (see table below).

7 Daily swabs will be collected from vaccination through D113. Swabs will be returned via drop-off location(s) specified by the clinic or through the mail.

8 COVID-19 Symptom Check to be performed within 24 hours prior to vaccination.

The following **additional** procedures will occur for Main cohort, immediate vaccination participants, who fall under any of the following categories:

- tested positive for SARS-CoV-2 from enrollment through Month 4 (see Section 9.7)
- enrolled also in the PCC cohort and are related to an index case (see Section 9.8)
- enrolled also in the CACC cohort (see Section 9.9)

Day relative to notification of infection:	D1-14
Study procedures	
Symptom tracking via eDiary	daily
Research Samples	
Serum for SARS-CoV-2 clinical serology ¹	✓ ²

¹ For blood self-collected by a participant the maximum volume will be less than 1 mL in a single collection.

² Sample for serology will be collected as soon as possible following report of positive SARS-CoV-2 test.

In addition, we may ask participants to sign a release to allow us to review their COVID-19 related medical records.

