2.11 Trial design rationale

We are proposing a 2-arm randomized, controlled, open-label trial, augmented with an observational cohort. Individuals indifferent to receipt and timing of COVID-19 vaccination will be randomized to immediate vaccination at Months 0 and 1, or standard of care with vaccination given at Months 4 and 5, if not received off-study previously. Individuals who prefer not to be vaccinated will be enrolled in an observational ‘Vaccine Declined’ group; all these individuals are considered part of the ‘Main cohort’ (Figure 2-7). The design also includes two cohorts of contacts of main study cohort participants – the Prospective Close Contact (PCC) cohort and the Case-Ascertained Close Contact (CACC) cohort – to allow capture of secondary transmission events.

[figure not shown]

Figure 2-7 Main cohort study design

Participants in the main study will self-collect nasal swabs daily in order to capture all incident SARS-CoV-2 infection events over 4 months of follow-up and to capture the full course of viral shedding – from onset of infection to viral clearance – among those with both asymptomatic and symptomatic infection.

To minimize participant burden and maximize study efficiency, as many study procedures as possible will be conducted remotely (not requiring an in-person visit) and electronically, such as initial screening and consent. Participants diagnosed with SARS-CoV-2 infection will complete daily e-diaries to capture symptoms.

Given that primary analyses will be conducted among baseline seronegative participants, the rate of baseline SARS-CoV-2 seropositivity will be monitored operationally with an operational target of no more than 10% for the main study cohort.

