Following completion of all procedures in the preceding list, and if results indicate that vaccination may proceed, vaccination is prepared and administered, per Moderna EUA Fact Sheet and Full Prescribing Information for Vaccination Providers that can be accessed at <https://www.modernatx.com/covid19vaccine-eua/>).

- End of study questionnaire at Month 5 (Visit 6)

For participants who have already received COVID-19 vaccination outside of study prior to Month 4 (Visit 5) visit or who decline vaccination, the following procedures are performed at Visit 5; Visit 6 will not occur (see [Appendix F](#)):

- Specimen collection
- End of Study questionnaire

9.7 Procedures for Main Cohort participant diagnosed with a SARS-CoV-2 infection during the study

If a participant is diagnosed with a SARS-CoV-2 infection during the course of the study, CDC guidelines on administration of vaccination will be followed.

Main Cohort participants who are clinically diagnosed with SARS-CoV-2 infection (from any test result indicative of acute infection) are referred to as clinically diagnosed index cases. They will be instructed to isolate per local guidelines and the following procedures will be performed:

- eDiary collection of daily symptoms of COVID-19 and assessment of whether clinical care was sought or hospitalization occurred (via self-report and/or request for medical records) through an eDiary for a period of 14 days or until symptoms have resolved, whichever is longer
- Daily nasal swabbing continued per schedule of procedures (see [Appendix E](#))
- Blood collection by phlebotomist or participant for SARS-CoV-2 clinical serology
- Close contacts identification (see Section [9.9](#))

Following resolution of the isolation period, participants will continue scheduled study visits. Follow-up duration for participants diagnosed with moderate or severe COVID-19 disease may be adjusted in consultation with the CRS (eg, to avoid interference with participant initiation of SARS-CoV-2 treatment).

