Appendix F Procedures for Main Cohort, Standard of Care and Vaccine Declined Groups

Visit: Day: Week: Month: Procedure	01 ¹ Scr.	02 D1 W0 M0	03 D29 W4 M1	04 D57 W8 M2	05 D113 W16 M4 VAC1	06 D141 W20 M5 VAC2
Study procedures						
Screening consent (if used)	✓	–		–	–	–
Assessment of understanding	✓	–		–	–	–
Protocol consent (eConsent)	✓	–		–	–	–
Medical history questionnaire ²	✓	✓		–	–	–
SARS-CoV-2 infection risk assessment ²	✓			Weekly		–
COVID-19 symptom surveillance ²	–			Weekly		–
Confirm eligibility	✓	–		–	–	–
Obtain demographics ²	✓	–		–	–	–
Randomize, Standard of Care Group only	–	✓		–	–	–
SARS-CoV-2 testing questionnaire ²	–			approximately 2x per week		–
End of study questionnaire ²	–	–		–	✓ ⁷	✓
Research Samples						
Serum for SARS-CoV-2 clinical serology ³	–	✓		✓	✓	–
Nasal swab	–			Daily ⁴		–
Vaccination procedures⁶						
COVID-19 symptom check ⁵	–	–		–	✓	✓
Vaccination	–	–		–	✓	✓

Greyed out visit does not apply to this group.

1 Screening may occur over the course of several contacts/visits up to and including day 1, prior to randomization.

2 Results from screening at school, if applicable, or at other locations will be captured via eDiary, please see Section 9.16.

3 From screening to the final study visit, the total blood volume to be collected from each participant will be approximately 15 mL (maximum) with a maximum of approximately 5 mL collected in a single visit. For blood self-collected by a participant the maximum volume will be less than 1 mL in a single collection. If a Main cohort participant is also in the Prospective Close Contact (PCC) cohort related to an index case or in the Case-ascertained Close Contact (CACC) cohort, one additional blood collection (self-collection) will be performed (see table below).

4 Daily swabs will be collected from D1 through D113. Swabs will be returned via drop-off location(s) specified by the clinic or through the mail.

5 COVID-19 Symptom Check to be performed within 24 hours prior to vaccination.

6 Vaccination procedures only apply to participants who have not received COVID-19 vaccine outside the study and for participants in the Vaccine Declined Group who request to be vaccinated.

7 Only applies to participants who are not receiving vaccination on study, ie, who have already received COVID-19 vaccine outside the study or who have declined vaccination (Visit 5 will be the last study visit for these participants).

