7.3 To evaluate the vaccine effect on SARS-CoV-2 viral load

Given the early termination, the study is underpowered to look at the vaccine effect on viral load. Therefore a limited, descriptive analysis will be performed. Descriptive statistics for peak viral loads on the cycle threshold (CT) scale among FAS-P acquisitions (censored at outside vaccination) will be tabulated by lab (Corteva vs. UW/Northwell), target (N1 and N2) and arm. Peak viral load will be defined as the minimum observed CT per participant, lab and target. Participants with CT data from both labs will be excluded. Descriptive statistics will include N, mean, minimum, median, quartiles and median. Results are stratified by lab to address potential differences between labs. We will also present the descriptive statistics for the number of days with a positive study PCR (qualitative) per participant among FAS-P acquisitions, broken down by arm.

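### SAP 7.3 counts PCR-positive days as complete although swabbing stops on a fixed day, and the protocol gives two different lengths for the daily symptom diary

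*Protocol*

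**What the plan says.** **Swabs.** Protocol Section 2.11 gives the purpose of daily swabbing over 4 months of follow-up as to "capture the full course of viral shedding – from onset of infection to viral clearance". The schedules fix the end: "Daily swabs will be collected from vaccination through D113" (Appendix E, Immediate Vaccination) and "Daily swabs will be collected from D1 through D113" (Appendix F, Standard of Care and Vaccine Declined). After a diagnosis, Section 9.7 says "Daily nasal swabbing continued per schedule of procedures" and cites Appendix E only. The add-on tables for participants who "tested positive for SARS-CoV-2 from enrollment through Month 4" list symptom tracking and one serum sample, with no swab row.

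**SAP.** Section 3.2.7 treats swabs as no longer expected after the earliest of the day before study completion, 111 days after enrollment and 31 December 2021, and also after outside vaccination or termination. Section 7.3 limits viral load to description: minimum CT, and the "number of days with a positive study PCR (qualitative) per participant" by arm.

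**Diary.** After a positive test, Section 9.7 requires daily symptom entries "for a period of 14 days or until symptoms have resolved, whichever is longer". Sections 9.8 and 9.9 give the same rule for the contact cohorts. The add-on tables in Appendices E and F show D1-14, and Appendices G and H show 14 days.

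**The concern.** Shedding duration and area under the curve belong to secondary endpoint 4, and the count of positive days is what the current SAP keeps of the duration endpoint. If swabbing ends on a fixed day, an infection found late contributes only the days left in the window, and the count records that as its full length. Such truncation shortens duration in both arms, and it takes more from the arm that sheds longer, so a true difference is pulled toward zero. A reader of the SAP table could not tell how many participants were still positive when observation ended.

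The diary conflict is of another kind. One operational rule has two lengths, so sites or cohorts could follow different rules for illnesses lasting beyond 14 days.

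**Working it through.** **Step 1. Reproduce the plan's viral-load power.** Inputs (Protocol 6.1.1): 225 post-Day 29 events, SD 1.8, a 1-log10 difference, one-sided 0.025. At VE_S 50% the split is 150 and 75.

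z = 1 / (1.8 × √(1/150 + 1/75)) − 1.96 = 3.93 − 1.96 = 1.97, so power is 97.5% against the stated 96.9%. At VE_S 70% (173 and 52) it is 94.0% against 93.5%. Both agree with the plan's simulations.

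**Step 2. Share of infections cut short.** Inputs (Table 6-2): 4% incidence and 5% loss over 16 weeks, both at constant rates. Daily hazards are h = −ln(0.96)/112 = 0.000364 for infection, halved for the vaccinated group at VE_S 50%, and l = −ln(0.95)/112 = 0.000458 for loss. The documents give no time to clearance, so k is an assumption. With λ = h + l, the share first positive in the last k of 112 days is

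[e^(−λ(112−k)) − e^(−112λ)] / [e^(−λa) − e^(−112λ)],

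where a = 0 for all infections and a = 28 for post-Day 29 infections.

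| k (assumed days to clearance) | All infections | Post-Day 29 | Of the planned 225 |
|---|---|---|---|
| 7 | 6.0% | 8.1% | 18 |
| 14 | 12.0% | 16.2% | 36.5 |
| 21 | 18.1% | 24.4% | 55 |

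The plain ratios are close: 14/112 = 12.5% and 14/84 = 16.7%. Post-Day 29 shares are nearly equal by arm (at k = 14, 16.2% unvaccinated and 16.3% vaccinated). SAP 7.3 covers all FAS-P acquisitions, so the first column is the more relevant one.

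**Step 3. Effect on a contrast in duration.** If first positives are spread evenly over T days and true duration is d, mean observed duration is d − d²/(2T). Take a true 14 versus 7 days (illustrative).

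- T = 112: 14 − 196/224 = 13.13 and 7 − 49/224 = 6.78. The difference is 6.34 instead of 7, a loss of 9.4%.
- T = 84: 14 − 196/168 = 12.83 and 7 − 49/168 = 6.71. The difference is 6.13, a loss of 12.5%.

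**Step 4. Effect on peak viral load.** If the peak comes 3 to 5 days after the first positive (assumed), 3.5% to 5.8% of post-Day 29 infections (8 to 13 of 225) could be cut before it. Dropping them moves the Step 1 power from 97.5% to between 97.1% and 96.8%, or from 94.0% to between 93.2% and 92.6% at VE_S 70%.

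**Step 5. The calendar stop.** 31 December 2021 is day 365 of the year, and 365 − 111 = 254, which is 11 September. For anyone enrolled after that date, swabs cease to be expected before 111 days. The shares above ignore this and the other SAP stops, because the documents give no infection dates.

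**Step 6. The diary, side by side.**

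| Cohort | Text | Table |
|---|---|---|
| Main | 9.7: longer of 14 days and resolution | Appendices E, F: D1-14 |
| PCC | 9.8: same | Appendix G: 14 days |
| CACC | 9.9: same | Appendix H: 14 days |

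The two columns agree only for illnesses that resolve within 14 days.

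**The case against.** A reader might infer that the protocol promises swabbing until clearance and then breaks the promise. The documents do not support that. Section 2.11 states an aim, in the same sentence as the 4-month limit, and the operative rule in Section 9.7 sends swabbing back to the schedule, which agrees with D113. The fixed stop is a design choice. What remains is that its consequence is not handled in the analysis.

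A reader might also infer that participants with long illnesses lose monitoring. That goes too far. Weekly symptom surveillance (Section 9.15) runs through follow-up and no passage stops it after a positive test. Section 9.7 also allows medical-record requests and adjusted follow-up for moderate or severe disease. Only the daily diary is in question. The Appendix E and F tables refer back to Section 9.7, so they can be read as shorthand for it, but a table showing D1-14 does not say so.

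Third, Protocol 6.4.4 already allows a model-based peak and a model-based duration, which could reach beyond the last swab. That is fair, but SAP 7.3 carries neither forward.

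Finally, the study stopped early, SAP 2.5 calls it underpowered, and SAP 7.3 makes no formal comparison. This lowers the stakes, and 225 events is a planning figure only. It does not make a count of positive days complete for someone still positive when swabbing ended.

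**Conclusion.** Two limited points stand.

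1. The daily-diary passages disagree in all the cohorts and must be reconciled. The SAP disease endpoint is unaffected, because Section 9.2 looks no further than 14 days after the first positive swab.
2. The count of PCR-positive days is right-truncated for late infections and the SAP does not say so. The D113 stop alone affects roughly 6% to 18% of all infections, or 8% to 24% of post-Day 29 infections, for an assumed 7 to 21 days to clearance. A 14 versus 7 day contrast is attenuated by about 9% to 12.5%. These figures rest on constant incidence and full daily swabbing up to D113.

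It would be tempting to conclude that primary endpoint 2 is compromised. Step 4 does not support that: under the planning assumptions, power for peak viral load falls by less than one and a half percentage points.

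**What to change.** **SAP 7.3.**

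- Replace or supplement the raw count with time from first positive study PCR to clearance, summarised by Kaplan-Meier by arm and right-censored at the last swab when that swab is still positive. State in advance what counts as clearance, for example the first negative result with no later positive.
- Report by arm the number still positive at the last swab. Stops at outside vaccination may not fall equally across arms.
- Show peak CT with and without participants first positive shortly before their last swab, with the cut-off fixed beforehand (5 days would match the upper end of the range assumed above).

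**Protocol.** Reconcile Sections 9.7 to 9.9 with the tables in Appendices E to H on diary length. If the text cannot be changed now, record which rule was applied in each cohort.

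**Cost.** One extra descriptive table from data already held, with few events, so wide intervals. Swabbing beyond D113 is not proposed: it would add procedures to a finished study and would overlap the Standard of Care vaccination offer at D113.

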Appendix F Procedures for Main Cohort, Standard of Care and Vaccine Declined Groups

Visit: Day: Week: Month: Procedure	01 ¹ Scr.	02 D1 W0 M0	03 D29 W4 M1	04 D57 W8 M2	05 D113 W16 M4 VAC1	06 D141 W20 M5 VAC2
Study procedures						
Screening consent (if used)	✓	–		–	–	–
Assessment of understanding	✓	–		–	–	–
Protocol consent (eConsent)	✓	–		–	–	–
Medical history questionnaire ²	✓	✓		–	–	–
SARS-CoV-2 infection risk assessment ²	✓			Weekly		–
COVID-19 symptom surveillance ²	–			Weekly		–
Confirm eligibility	✓	–		–	–	–
Obtain demographics ²	✓	–		–	–	–
Randomize, Standard of Care Group only	–	✓		–	–	–
SARS-CoV-2 testing questionnaire ²	–			approximately 2x per week		–
End of study questionnaire ²	–	–		–	✓ ⁷	✓
Research Samples						
Serum for SARS-CoV-2 clinical serology ³	–	✓		✓	✓	–
Nasal swab	–			Daily ⁴		–
Vaccination procedures⁶						
COVID-19 symptom check ⁵	–	–		–	✓	✓
Vaccination	–	–		–	✓	✓

Greyed out visit does not apply to this group.

1 Screening may occur over the course of several contacts/visits up to and including day 1, prior to randomization.

2 Results from screening at school, if applicable, or at other locations will be captured via eDiary, please see Section 9.16.

3 From screening to the final study visit, the total blood volume to be collected from each participant will be approximately 15 mL (maximum) with a maximum of approximately 5 mL collected in a single visit. For blood self-collected by a participant the maximum volume will be less than 1 mL in a single collection. If a Main cohort participant is also in the Prospective Close Contact (PCC) cohort related to an index case or in the Case-ascertained Close Contact (CACC) cohort, one additional blood collection (self-collection) will be performed (see table below).

4 Daily swabs will be collected from D1 through D113. Swabs will be returned via drop-off location(s) specified by the clinic or through the mail.

5 COVID-19 Symptom Check to be performed within 24 hours prior to vaccination.

6 Vaccination procedures only apply to participants who have not received COVID-19 vaccine outside the study and for participants in the Vaccine Declined Group who request to be vaccinated.

7 Only applies to participants who are not receiving vaccination on study, ie, who have already received COVID-19 vaccine outside the study or who have declined vaccination (Visit 5 will be the last study visit for these participants).

The following **additional** procedures will occur for Main cohort, standard of care and vaccine declined participants, who fall under any of the following categories:

- tested positive for SARS-CoV-2 from enrollment through Month 4 (see Section [9.7](#))
- enrolled also in the PCC cohort and are related to an index case (see Section [9.8](#))
- enrolled also in the CACC cohort (see Section [9.9](#))

Day relative to notification of infection:	D1-14
Study procedures	
Symptom tracking via eDiary	daily
Research Samples	
Serum for SARS-CoV-2 clinical serology ¹	✓ ²

¹For blood self-collected by a participant the maximum volume will be less than 1 mL in a single collection.

² Sample for serology will be collected as soon as possible following report of positive SARS-CoV-2 test

In addition, we may ask participants to sign a release to allow us to review their COVID-19 related medical records.

Appendix G Procedures for Prospective Close Contact (PCC) cohort

	Visit: Day: Month:	100 D1 M0	101 D113 M4
		Enrollment	Follow-up
Study procedures			
Protocol consent (eConsent)		✓	–
Obtain demographics ¹		✓	–
SARS-CoV-2 testing questionnaire ¹		approximately 2x per week	
End of study questionnaire ¹		–	✓

¹ Results from screening at school, if applicable, or at other locations will be captured via eDiary, please see Section [9.16](#).

If a PCC participant (or their Main study contact) tests positive for SARS-CoV-2, the following **additional** procedures will occur:

Day relative to notification of infection:	D1	D29
Study procedures		
Report of exposure ¹	✓	
Symptom tracking ¹	Daily for 14 days	–
Research Samples		
Serum for SARS-CoV-2 clinical serology ²	✓	✓
Nasal swab ³	Daily for 14 days	–

¹ Will be captured via eDiary , please see Section [9.16](#).

²For blood self-collected by a participant the maximum volume will be less than 1 mL in a single collection. Sample for serology will be collected as soon as possible following report of positive SARS-CoV-2 test.

³Swabs will be returned via drop-off location(s) specified by the clinic or through the mail. Nasal swabs will be collected as soon as possible following report of positive SARS-CoV-2 test.

In addition, we may ask participants to sign a release to allow us to review their COVID-19 related medical records.

Appendix H Procedures for Case-Ascertained Close Contact Cohort

	Visit: 200	201	202
	Day: D1	D1-D3	D29
	Month: M0	M0	M1
	Enrollment	Initial specimen collection	Follow-up
Study procedures			
Protocol consent (eConsent)	✓	–	–
Collection of demographic information ¹	✓	–	–
Report of exposure ¹	✓	–	–
Symptom tracking ¹		Daily for 14 days	–
SARS-CoV-2 testing questionnaire ¹		approximately 2x per week	
End of study questionnaire ¹	–	–	✓
Research Samples			
Serum for SARS-CoV-2 clinical serology ²		✓	✓
Nasal swab ³		Daily for 14 days	–

¹Results from screening at school, if applicable, or at other locations will be captured via eDiary, please see Section 9.16.

² For blood self-collected by a participant the maximum volume will be less than 1 mL in a single collection. Sample for serology will be collected as soon as possible following report of positive SARS-CoV-2 test (ie, as early as Day 1).

³Swabs will be returned via drop-off location(s) specified by the clinic or through the mail. Nasal swabs will be collected as soon as possible following report of positive SARS-CoV-2 test (ie, as early as Day 1).

In addition, we may ask participants to sign a release to allow us to review their COVID-19 related medical records.

